## 9.4.1. PK/PD Unblinding Plan

If needed, a PK/PD unblinding plan will be developed to safeguard the study blind for members of the study team. These procedures will be in accordance with applicable Pfizer SOPs for releasing randomization codes and breaking the study blind. Under this plan, a limited number of individuals, not on the study team, will be unblinded, with the purpose of composing PK/PD and/or immunogenicity analysis sets and conducting PK/PD analysis that will not be made available to the study team until after database lock.

## 9.5. Sample Size Determination

A sufficient number of participants will be screened to achieve a total of approximately 168 participants, with 42 participants randomly assigned to ponsegromab 100, 200 or 400 mg and placebo in approximately a 1:1:1:1 ratio. This is expected to ensure completion through Week 12 of the study of approximately 120 completing participants (30 in each of ponsegromab 100, 200 or 400 mg and placebo), assuming a discontinuation rate of approximately 30% (if this rate is higher, or there is a high rate of non-compliance, more participants may be randomized to ensure the required number of completing participants).

The sample size in the ponsegromab and placebo arms is based on the primary efficacy endpoint, mean change from baseline in body weight at Week 12. An informative meta-analytic predictive prior, based on historical results from internal and external studies, robustified by the inclusion of a weakly informative component to handle any possible prior-data conflict, will be used for the placebo response and is expected to equate to an effective sample size of 39 placebo participants. Further details on the prior derivation will be given in the statistical analysis plan SAP.

120 completing participants, in a 1:1:1:1 ratio, plus 39 participants from the placebo prior, gives acceptable Operating Characteristics in that:

- The probability of achieving statistical significance (at the 5% significance level, using a 1-sided t-test), for a true difference between ponsegromab and placebo of 2.7 kg, is approximately 80%.
- An observed difference between ponsegromab and placebo of 1.8 kg is expected to achieve statistical significance (at the 5% significance level, using a 1-sided t-test).

A conservative estimate of the standard deviation, for the change from baseline in body weight at 12 weeks of 4.9 has been used.

The sample size determination has been performed using pairwise comparisons. This is considered to be a conservative approach since the primary analysis will utilize a Bayesian  $E_{max}$  dose-response model, which would be anticipated to best describe the dose-response in the presence of an effective compound.

Evaluable participants are defined as in Section 9.2. Participants who withdraw from the study will not be replaced.

Of the approximately 168 planned randomized participants, up to approximately 36 are planned to be randomized (to ponsegromab 100, 200 or 400 mg and placebo in approximately a 1:1:1:1 ratio) into the additional PK substudy. This sample size has been chosen empirically to provide sufficient data to adequately characterize ponsegromab PK and GDF-15 effect and PK/PD relationship in cancer patients with cachexia and elevated concentrations of GDF-15.

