#### 9.3.2. Primary Endpoint Analysis

The primary endpoint analysis will be a Bayesian  $E_{max}$  model applied to results from an MMRM analysis.

Change from baseline in body weight at Week 12 will first be analyzed using Estimand 1 and an MMRM model (as per Section 9.3.1.1). The MMRM model will be fitted to the change from baseline at all post-treatment dosing timepoints up to Week 12 (ie, Weeks 4, 8, and 12) using the Censored analysis set. Additional terms for type of therapy [ie, platinum or not] and type of cancer will be fitted in the model. Least squares means (and 90% CIs) and mean differences versus placebo (and 90% CIs and p-values) will be provided.

A Bayesian  $E_{max}$  model will then be fitted to the Week 12 LSmeans and SEs from the MMRM analysis. The predicted  $ED_{50}$  for the compound ( $P_{50}$ ) is currently ~150 mg Q4W dose, based on latest data for the compound (this may be updated as new data become available). Prior distributions for the placebo response ( $E_0$ ), the difference in response (difTarget) between the highest dose (400 mg) and placebo, and the residual standard deviation (*sigma*) are:

 $E_0$ : An informative meta-analytic predictive prior, based on historical results from internal and external studies, robustified by the inclusion of a weakly informative component to handle any possible prior-data conflict, will be used for the placebo change from baseline at Week 12. This will be approximated by a t-distribution with a mean of -0.58 kg, an SD of 1.84 kg and 3 degrees of freedom. If additional relevant data become available during the study, a sensitivity analysis may be performed by incorporating the new data, using the same approach as above. Further details on the prior derivation will be given in the statistical analysis plan (SAP).

*difTarget*: A vague t-distribution will be used for the 400 mg placebo-corrected change from baseline at Week 12 with a mean of 0, a SD equal to 10 times the predicted standard deviation (ie, 49 kg) and 5 degrees of freedom.

*sigma*: A uniform prior will be used, with a range we are confident will include the population value. A lower bound of 0.49 kg and an upper bound of 49 kg will be used.

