Appendix 5. Bayesian Emax Model Methodology Details

Data Provided by Programmer

A .csv dataset of LS means from the MMRM analysis should be produced by programming for use in R by the reporting statistician and QC statistician. The file should be in the following format (Note that column headers should be labelled as specified below (including capitalization), as R is case sensitive): -

Dose	Mean	SE
0	0	0.3
2.5	0.2	0.4
10	0.4	0.5
40	0.3	0.3
80	1.6	0.4
120	1.8	0.5

The residual standard deviation (Residual_SD) on Week 12 from the unstructured covariance matrix from the MMRM will also be provided by programming in a separate .csv file.

Fitting the Emax Model

The 4-parameter Emax model will be fitted using the latest version (currently 2.3.5) of the clinDR package. This analysis will be conducted by the reporting statistician. A different statistician will conduct QC of the analysis. The outputs of the analysis will be provided as .csv files to the programming team for creation of programming tables and figures.

The default burn-in and number of samples will be utilized along with thinning of 20, which will include 3 chains to assess convergence.

Model diagnostics will be examined, including trace and auto-correlations plots. If these raise concerns over model convergence, additional burn-ins, samples and thinning will be investigated to improve convergence. Changes to the priors below may also be considered (e.g. increase precision of hill) to improve convergence, if deemed necessary, and would be documented in final tables as appropriate. The final diagnostic plots will not be included in the clinical study report.

Priors Priors

Prior distributions will be specified for the placebo response (E_0), the difference in response (difTarget) between the highest dose (dTarget = 400mg) and placebo, and the residual standard deviation (sigma). Note that Emax is derived from other parameters and is thus not explicitly supplied.

Parameter	Prior
E ₀	t(Mean = -0.58, SD = 1.84, df=3)
difTarget	t(Mean = 0, SD = 49, df=5)
sigma	Uniform(lb=0.49, ub=49)

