*E*₀: An informative meta-analytic predictive prior, based on historical results from internal and external studies, robustified by the inclusion of a weakly informative component to handle any possible prior-data conflict, will be used for the placebo change from baseline at Week 12. This will be approximated by a t-distribution with a mean of -0.58 kg, an SD of 1.84 kg and 3 degrees of freedom. If additional relevant data become available during the study, a sensitivity analysis may be performed by incorporating the new data, using the same approach as above.

difTarget: A vague t-distribution will be used for the 400 mg placebocorrected change from baseline at Week 12 with a mean of 0, a SD equal to 10 times the predicted standard deviation (ie, 49 kg) and 5 degrees of freedom.

sigma: A uniform prior will be used, with a range we are confident will include the population value. A lower bound of 0.49 kg and an upper bound of 49 kg will be used.

ClinDR default settings will be used to specify prior distributions for the Hill parameter and the ED₅₀. The default distributions in the current version of clinDR (version 2.3.5) are based on a meta-analysis of clinical dose response data and are listed below. These default distributions will be updated if the meta-data, and their analysis, are updated before the completion of the current study.

Parameter	Prior
log(ED ₅₀)	log(P ₅₀) + t(Mean=0, SD=1.73, df=5)
log(Hill)	t(Mean = 0, SD =0.85, df=5)

The correlation between these two parameters is currently -0.45 based on the analysis of the meta-data, which also would be updated if the historical analysis is updated.

The predicted ED₅₀ for the compound (P_{50}) is currently ~150 mg Q4W dose, based on latest data for the compound (this may be updated as new data become available).

R Code

The following R code is included as an example that will be used as a basis for the analysis:

library(clinDR) mmrmRes <- read.csv("LSmeans.csv", header=T, stringsAsFactors=F)

Determine 'effective' subject numbers based on MMRM SD at Week 12: mmrm_sd <- 0.825 # Provided by programming mmrmRes\$n <- trunc((mmrm sd/mmrmRes\$se)^2,0)

```

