# Set-up priors and MCMC options:
prior mmrm <- emaxPrior.control(epmu=-0.58, epsca=1.84.

                            difTargetmu=0, difTargetsca=49,
                            dTarget=400, effdf=5.
                            p50=150.
                            sigmalow=0.49, sigmaup=49)
mcmc mmrm <- mcmc.control(chains=3, thin=20, seed=169)

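### The sample size credits the placebo prior with 39 participants, but the t prior specified for the analysis is worth 7 to 28, and the example code does not clearly implement that prior

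*Protocol*

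**What the plan says.** Protocol 9.5 sizes the trial by pairwise comparisons: 30 completers per arm, SD 4.9 kg, one-sided 5% t-test. The placebo prior "will be used for the placebo response and is expected to equate to an effective sample size of 39 placebo participants". With these 39 added, the section claims about 80% power for a true difference of 2.7 kg, and states: "An observed difference between ponsegromab and placebo of 1.8 kg is expected to achieve statistical significance". The Synopsis repeats the 39 and the 80%. On how the prior was built, 9.5 says: "Further details on the prior derivation will be given in the statistical analysis plan SAP".

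Protocol 9.3.2 then fixes the prior that enters the primary Emax model: "This will be approximated by a t-distribution with a mean of -0.58 kg, an SD of 1.84 kg and 3 degrees of freedom". The prior table in SAP Appendix 5 agrees: "t(Mean = -0.58, SD = 1.84, df=3". The accompanying text in Appendix 5 repeats the protocol's description. It gives no mixture components or weights, no definition of effective sample size (ESS), and no ESS for the t approximation.

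Appendix 5 introduces its code with: "The following R code is included as an example that will be used as a basis for the analysis". The prior call enters "epmu=-0.58, epsca=1.84" for placebo and, as its only degrees of freedom, "dTarget=400, effdf=5".

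**The concern.** The 39 and the t-distribution are presented as the same prior, but they do not carry the same information. The operating characteristics in 9.5 belong to a prior worth 39. None are given for the prior that will be analysed.

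The example code leaves the weight of that prior open in two respects. The 3 degrees of freedom stated for E0 appear nowhere in it; the single value of 5 matches what is stated for difTarget. And 1.84 is passed as `epsca`, while neither document says whether that argument takes an SD or a scale. For a t-distribution with 3 degrees of freedom, the SD is √3 times the scale, so the two readings give quite different priors.

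Every dose-versus-placebo contrast in the primary analysis depends on E0. How strongly the placebo estimate is drawn towards −0.58 kg should therefore be fixed before anyone sees unblinded data.

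**Working it through.** **Inputs.** Protocol 9.5: 30 completers per arm, SD 4.9 kg, one-sided 5%, true difference 2.7 kg, ESS 39. Protocol 9.3.2 and SAP Appendix 5: t prior, mean −0.58 kg, SD 1.84 kg, 3 df. Appendix 5 code: `epsca` 1.84, `effdf` 5.

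**1. The plan's own figures.** For 30 active against 30 + 39 = 69 placebo:

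- SE = 4.9 × √(1/30 + 1/69) = 1.072 kg
- threshold = t(0.95; 97 df) × SE = 1.661 × 1.072 = 1.78 kg
- power, noncentral t with noncentrality 2.7/1.072 = 2.52: 80.4%

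This reproduces the stated 80% and 1.8 kg. With 30 against 30, SE = 1.265 kg, the threshold is 2.11 kg and power is 67.9%. The stated figures therefore need the 39.

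**2. What the t prior is worth.** With df ν and scale s, the SD is s√(ν/(ν−2)). An SD of 1.84 with 3 df gives s = 1.84/√3 = 1.062. ESS at an outcome SD of 4.9 (4.9² = 24.01):

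- variance match: 24.01/1.84² = 7.1
- expected information: 24.01 × (ν+1)/[(ν+3)s²] = 24.01 × 4/(6 × 1.129) = 14.2
- gain in posterior precision with 30 placebo observations centred on the prior mean (numerical): 20.7
- information at the mode: 24.01 × (ν+1)/(νs²) = 24.01 × 4/(3 × 1.129) = 28.4

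A normal prior worth 39 would have SD 4.9/√39 = 0.785 kg. The same four measures for each reading of the code:

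| Prior | Variance | Expected information | Posterior gain | Mode |
|---|---|---|---|---|
| SD 1.84, 3 df (as stated) | 7.1 | 14.2 | 20.7 | 28.4 |
| SD 1.84, 5 df | 7.1 | 8.9 | 12.3 | 14.2 |
| Scale 1.84, 3 df | 2.4 | 4.7 | 8.1 | 9.5 |
| Scale 1.84, 5 df | 4.3 | 5.3 | 7.7 | 8.5 |

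None reaches 39.

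**3. Power and threshold computed directly.** Flat prior on the active mean, the listed prior on placebo, success if the posterior probability of a positive difference exceeds 0.95, true placebo mean −0.58 kg (no prior-data conflict). The threshold assumes SD known and an observed placebo mean of −0.58 kg. The SD-estimated column comes from 20,000 simulations (Monte Carlo SE 0.3 points). The pull is the shift of the placebo estimate towards the prior mean when the observed placebo mean is 1 kg away from it.

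| Prior on placebo | Power, SD known | Power, SD estimated | Threshold (kg) | Pull (kg) |
|---|---|---|---|---|
| Normal, worth 39 | 83.2% | 82.4% | 1.76 | 0.565 |
| SD 1.84, 3 df (as stated) | 78.1% | 77.8% | 1.86 | 0.39 |
| SD 1.84, 5 df | 75.6% | 74.8% | 1.92 | 0.28 |
| Scale 1.84, 3 df | 73.6% | 72.3% | 1.97 | 0.20 |
| Flat | 68.8% | 67.6% | 2.08 | 0 |

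Like for like, moving from a prior worth 39 to the three t priors costs about 5, 8 and 10 points of power.

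**4. Could both numbers be right?** The mixture is not given, so one was assumed: 88% normal with SD 0.694 plus 12% normal with SD 4.9. Its expected-information ESS is 39 and its overall SD is 1.82 kg, with power 83.4% and threshold 1.74 kg (SD known). So 39 and 1.84 can describe one mixture. A t-distribution matched to the SD then loses the concentration that made the mixture worth 39.

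**The case against.** The sum in 9.5 is correct for its inputs, and 39 may be a correct description of the mixture before approximation. Both points stand: what fails is carrying 39 over to a different distribution.

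The range of 7 to 28 reflects four definitions. The posterior-gain figure of 20.7 is arguably closest to how 9.5 uses the number. That is fair, but no definition gives 39.

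On the stated reading the practical loss is small: about 78% against approximately 80%, and 1.86 against 1.8 kg. The protocol calls 4.9 kg conservative, and the Phase 1b study reported 4.75 kg in 10 dosed participants. At 4.75 kg the stated t prior gives 80.1% and 1.81 kg. This limits the size of the problem, but 4.75 kg is not the planning assumption.

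The scale reading rests on software behaviour that the documents do not describe, so its figures are conditional. For SD versus scale, the code is not shown to match the text; it is not shown to differ. The degrees of freedom do conflict on the page. The code is only an example, with some placeholder values, but it carries the trial's own prior values and is the declared basis for the analysis.

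Finally, 9.5 considers pairwise sizing conservative relative to the Emax model, SAP 6.1.1.2 plans a sensitivity analysis with a vague E0 prior, and the MMRM results use no prior. These will make dependence on the prior visible. They do not settle which informative prior is primary.

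**Conclusion.** The concern holds and should be fixed. The 39 in Protocol 9.5 and the Synopsis is not the ESS of the prior specified for the analysis, which is worth 7.1 to 28.4 participants at SD 4.9 kg if 1.84 is an SD with 3 df. On that reading the 80% nearly holds, and it is the ESS and the threshold that clearly slip. If the code's 5 df were used, the ESS range would fall to 7.1 to 14.2 and the pull at a 1 kg discrepancy from 0.39 to 0.28 kg. If 1.84 were also taken as a scale, the prior would be worth less than 10 participants.

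The power figures assume 30 completers per arm, SD 4.9 kg and a true placebo mean equal to the prior mean. They concern the pairwise calculation only. No shortfall is claimed for the Emax analysis, for which the documents give no operating characteristics, and no bias or type I error problem is claimed.

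**What to change.** Before unblinding:

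1. **SAP Appendix 5, code.** Confirm that 1.84 is the SD and enter it accordingly; if the argument takes a scale, SD 1.84 with 3 df is entered as 1.84/√3 = 1.06. Align the E0 degrees of freedom with the stated 3. Check in the same way how the difTarget value of 49, stated as an SD, is entered as `difTargetsca`.
2. **Protocol 9.5 and Synopsis.** Replace 39 with the ESS of the t prior actually used, naming the definition. Give pairwise power and threshold by direct calculation under that prior, with the no-prior figures beside them. If SD 1.84 and 3 df are confirmed, these are about 78% at 2.7 kg and about 1.9 kg; the t-test without the prior gives 68% and 2.1 kg.
3. **SAP Appendix 5, derivation.** Supply what 9.5 promised: the mixture, its ESS (39, if that is its source) and how the t-distribution was fitted to it. The prior should not be tightened to recover 39.

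The cost is wording in two protocol sections, a short derivation and two code arguments. The stated figures become slightly less favourable. If the code was meant literally as a scale, entering an SD gives the placebo prior more weight, so the choice must be made blind. No extra participants are needed.

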#### **10. SUPPORTING DOCUMENTATION AND OPERATIONAL CONSIDERATIONS**

#### 10.1. Appendix 1: Regulatory, Ethical, and Study Oversight Considerations

#### **10.1.1. Regulatory and Ethical Considerations**

This study will be conducted in accordance with the protocol and with the following:

- Consensus ethical principles derived from international guidelines, including the Declaration of Helsinki and CIOMS International Ethical Guidelines;
- Applicable ICH GCP guidelines;
- Applicable laws and regulations, including applicable privacy laws.

The protocol, protocol amendments, ICD, SRSD(s), and other relevant documents (eg, advertisements) must be reviewed and approved by the sponsor, submitted to an IRB/EC by the investigator, and reviewed and approved by the IRB/EC before the study is initiated.

Any amendments to the protocol will require IRB/EC approval before implementation of changes made to the study design, except for changes necessary to eliminate an immediate hazard to study participants.

Protocols and any substantial amendments to the protocol will require health authority approval prior to initiation except for changes necessary to eliminate an immediate hazard to study participants.

The investigator will be responsible for the following:

- Providing written summaries of the status of the study to the IRB/EC annually or more frequently in accordance with the requirements, policies, and procedures established by the IRB/EC;
- Notifying the IRB/EC of SAEs or other significant safety findings as required by IRB/EC procedures;
- Providing oversight of the conduct of the study at the site and adherence to requirements of 21 CFR, ICH GCP guidelines, the IRB/EC, European regulation 536/2014 for clinical studies, European Medical Device Regulation 2017/745 for clinical device research, and all other applicable local regulations.

## 10.1.1.1. Reporting of Safety Issues and Serious Breaches of the Protocol or ICH GCP

In the event of any prohibition or restriction imposed (ie, clinical hold) by an applicable regulatory authority in any area of the world, or if the investigator is aware of any new information that might influence the evaluation of the benefits and risks of the study intervention, Pfizer should be informed immediately.

In addition, the investigator will inform Pfizer immediately of any urgent safety measures taken by the investigator to protect the study participants against any immediate hazard, and of any serious breaches of this protocol or of the ICH GCP guidelines that the investigator becomes aware of.

## 10.1.2. Financial Disclosure

Investigators and subinvestigators will provide the sponsor with sufficient, accurate financial information as requested to allow the sponsor to submit complete and accurate financial certification or disclosure statements to the appropriate regulatory authorities. Investigators are responsible for providing information on financial interests during the course of the study and for 1 year after completion of the study.

## 10.1.3. Informed Consent Process

The investigator or the investigator's representative will explain the nature of the study, including the risks and benefits, to the participant or their legally authorized representative and answer all questions regarding the study. The participant or their legally authorized representative should be given sufficient time and opportunity to ask questions and to decide whether or not to participate in the trial.

Participants must be informed that their participation is voluntary. Participants or their legally authorized representative (if allowed by local regulations) will be required to sign a statement of informed consent that meets the requirements of 21 CFR 50, local regulations, ICH guidelines, privacy and data protection requirements, where applicable, and the IRB/EC or study center.

The investigator must ensure that each participant or their legally authorized representative is fully informed about the nature and objectives of the study, the sharing of data related to the study, and possible risks associated with participation, including the risks associated with the processing of the participant's personal data.

The participant or their legally authorized representative must be informed that their personal study-related data will be used by the sponsor in accordance with local data protection law. The level of disclosure must also be explained to the participant or their legally authorized representative.

The participant or their legally authorized representative must be informed that their medical records may be examined by Clinical Quality Assurance auditors or other authorized personnel appointed by the sponsor, by appropriate IRB/EC members, and by inspectors from regulatory authorities.

The investigator further must ensure that each study participant or their legally authorized representative is fully informed about their right to access and correct their personal data and to withdraw consent for the processing of their personal data.

The medical record must include a statement that written informed consent was obtained before the participant was enrolled in the study and the date on which the written consent was obtained. The authorized person obtaining the informed consent must also sign the ICD.

Participants or their legally authorized representative must be reconsented to the most current version of the IRB/EC-approved ICD(s) during their participation in the study as required per local regulations.

A copy of the ICD(s) must be provided to the participant or their legally authorized representative (if allowed by local regulations).

Participants who are rescreened are required to sign a new ICD.

